Chronic musculoskeletal pain is prevalent in later life and has a significant impact on older adults' physical and psychological well-being, including falls, fatigue, depression, and level of functioning. Poor sleep quality/disturbed sleep is a common coexisting condition in older adults with chronic musculoskeletal pain. Epidemiological studies have revealed that 67%-88% of people with chronic pain reported poor sleep. In addition, early research suggests a bidirectional relationship between sleep disturbances and pain and the association may be mediated by negative mood. Poorly managed chronic pain and sleep, particularly in the older adults, may result in multiple adverse health outcomes, including depression, social isolation, decreased mobility, cognitive impairment and increased healthcare utilization and cost. There is a discrepancy between the high prevalence of pain /disturbed sleep in the older adult population and the limited attention paid to these conditions in both research literature and clinical care.

Sedentary lifestyle, which is reported by 90% of older Americans, is an important risk factor for both chronic musculoskeletal pain and sleep disturbances. Older adults with a higher incidence of chronic pain are generally less physically active than others. Although, it is well recognized that physical activity/exercise is an effective intervention to improve sleep and reduce pain and improve function in a variety of pain conditions, traditional interventions to increase physical activity are challenging due to extensive staffing requirements and low adherence. Electronic activity monitors, such as wrist-worn accelerometers, can track heart rate, activity, and sleep to allow individuals to work towards their personal activity and sleep goals. These appealing features make these devices ideal for interventions that aim to change behaviors and improve health outcomes. However, the efficacy of using electronic activity monitors to promote physical activity and health in older adults has not been well examined. In addition, individually tailored physical activity interventions that account for an individual's preference and functional limitation have been proven to improve adherence and study outcomes.

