Our proposed theory-derived intervention is guided by theoretical constructs from the self-efficacy theory. Self-efficacy, one's confidence in the ability to perform particular behaviors, influences the performance of those behaviors, which in turn impacts health outcomes. Enactive mastery experiences, verbal persuasion, vicarious experiences, and physiological/ emotional status are the four principle sources of self-efficacy beliefs. Evidence illustrates that physical activity interventions designed based on self-efficacy concepts

effectively promote physical activity in older adults. The personalized behavioral intervention, which includes physical activity training, exercise prescription, goal setting, phone coaching, consultation, and feedback, real-time physical activity self-monitoring, interactive prompts and feedback with smartwatch, and weekly financial incentives will provide older adults with a stronger sense of self-efficacy. This will engage them in physical activity.

4. Study Procedures

Overview of study design: This is a two-group randomized controlled trial to test the effectiveness of a 12-week personalized behavioral intervention implementing smartwatch technology in promoting physical activity, pain, and sleep in older adults in comparison with a control group. We aim to enroll 20 eligible participants in one years and complete the study in 18 months. Length of a subject's participation time in study will be 16-18 weeks in total, which includes 2-3 week of screening and pre-intervention data collection, 12-week intervention/control period, and 2-3 week post-intervention data collection. It is an unblinded trial. Due to the nature of the intervention (ongoing communication between research team and participants), it is impossible to blind the group assignment from the participants and the research team.

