Self-monitoring: Subjects will self-monitor their level of physical activity (steps & minutes of moderate activity) using the smartwatch. The Google calendar and Fitbit apps will send messages and alerts to the subject's smartwatch that encourage them to achieve their daily goals. For example, a participant may typically be inactive for a long period (e.g., >90 minutes) at 10AM. In this case, the research assistant will program the smartwatch to pro-actively chime or vibrate at 10AM each day with a reminder message through Google Calendar. Similarly, if the smartwatch detects a long sedentary period, the Fitbit app will automatically send an alert via the smartwatch to motivate the subject to increase their physical activity. The smartwatch will be removed every 3-4 days for charging. If a participant has low activity for 3 consecutive days, the research assistant will call the participant to either encourage them to adhere to the plan or provide a modified plan after consulting the exercise trainer.

Phone consultation: Subjects will have biweekly phone consultation with the research team members to receive guidance and adjustment on activity plans. Recognizing that changing behavior is a process, the personalized activity plan will be less intense at the beginning and adjusted every two weeks based on participant's data during the previous two weeks.

Description of control condition: The control group will receive general education on physical activity for older adults and continue their daily activity and healthcare routine. They will also receive a Go4Life program book from the National Institute on Aging.

Data collection includes pre-intervention (baseline, 2weeks) and post-intervention (2weeks). The data collection will take place in a private room at the School of Nursing, a clinic office or the participant's apartment per the participant's preference.

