PROMIS measures will be used to assess multiple study outcomes. NINR Common data element of sleep, fatigue, anxiety, depression and cognition If a participant is significantly depressed (rating “Always” in all the 6 items that assess depressive symptoms) and not receiving any treatment for depression during assessments, we would share the information with the participant’s primary care provider and refer the participant for treatment with his/her primary care provider.

Functional Status: We will use the Katz Index of Independence in Activities of Daily Living (ADL) and The Lawton Instrumental Activities of Daily Living (IADL) Scale to measure older adult’s functional status.

Balance and gait speed will be measured using the Short physical performance battery (SPPB)

Other information includes age, race, body mass index, education, life style (tobacco and alcohol use, BMI), depression (GDS), pain, fatigue, medication use (antidepressant, benzodiazepine, pain and sleep medication), and number of medical conditions. Information will be collected via questionnaires.

The study will not interfere with the participants’ routine care. Participants in both groups will receive their routine care. The participants at both groups have the freedom to withdraw anytime from the study. The research team will remove the participants from the study if the research team cannot get contact with the participants for a month or the participant miss two appointments with the research team for no reason.

5. Inclusion/Exclusion Criteria

Key inclusion criteria include 60-85 years, intact cognition [[Montreal Cognitive Assessment \(MoCA\)>23](#)], poor quality of sleep (Insomnia Sleep Index>7), self-reported presence of pain, capacity for mild to moderate physical activity.

Participants will **be excluded** if they 1) have serious underlying illness (such as malignant neoplasms, infection, unexplained fever, weight loss, or recent trauma) causing their pain, 2) are non-ambulatory or have severely impaired mobility, 3) have visual or hearing impairment that interfered with assessments, and 4) have an acute or a terminal illness, 5) have neuropathic pain.

6. Drugs/ Substances/ Devices

N/A

7. Statistical analysis plan (SAP)

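### The only visible depression referral rule fires at the ceiling of the scale in untreated participants, and the GDS triggers no action

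*Combined protocol and SAP*

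**What the plan says.** The action rule stands in the PROMIS paragraph of Section 4 (Measurement). A participant counts as significantly depressed after rating 'Always' "in all the 6 items that assess depressive symptoms) and not receiving any treatment for depression during assessments". When both conditions hold, the team informs the participant's "primary care provider and refer the participant for treatment with his/her primary care provider". I take the six items to be the PROMIS depression items, because the rule sits in that paragraph.

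The GDS appears once, in the list of other information in the same section: "depression (GDS), pain, fatigue, medication use". No cut-off or action is attached to it. Section 4 has depression assessed at baseline and again at the post-intervention meeting, with no further rule at either point. No exclusion criterion in Section 5 names depression.

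Some general provisions also bear on the point. Section 4 states that "Participants in both groups will receive their routine care". Section 8 makes staff responsible for telling the PI about safety concerns, has the PI meet staff weekly and review each participant's safety, and provides an independent safety monitor who can be consulted at any time and who meets the PI quarterly.

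**The concern.** The Background says that poorly managed pain and sleep in older adults "may result in multiple adverse health outcomes, including depression, social isolation, decreased mobility, cognitive impairment", and every enrolled participant has both complaints. The team will hold answers on two depression scales. Only the maximum answer on every item of one of them obliges it to act. Because the protocol spells out what it means by significant depression, staff could reasonably read anything below that as needing no action. At stake is whether an untreated participant with very high depression answers is referred by rule or only if someone happens to raise it.

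**Working it through.** The plan gives no figure to reproduce. The check applies the stated rule, then asks what else in the text could lead to a referral.

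**1. The rule applied.** Referral is required only if 'Always' is given on 6 of 6 items and the participant is untreated.

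| Treated for depression? | 'Always' answers | GDS | Referral required? |
|---|---|---|---|
| No | 6 | any | Yes |
| No | 5 | any | No |
| Yes | 6 | any | No |

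The documents do not give the item scoring. If items run from 1 to 5 (an assumption), the trigger is 6 × 5 = 30. Five 'Always' answers plus one lower answer give 25 + 1 = 26 up to 25 + 4 = 29, and none of these scores triggers referral.

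**2. Time to the next depression assessment.** The design overview in Section 4 gives "2-3 week of screening and pre-intervention data collection, 12-week intervention/control period, and 2-3 week post-intervention data collection". The post-intervention meeting follows two weeks of Actigraph wear.
- Shortest: the baseline interview falls at the end of the pre-intervention block and the meeting as soon as recording ends, so 12 + 2 = 14 weeks (98 days).
- Longest: 3 + 12 + 3 = 18 weeks (126 days) would need the interview on the first day of participation. Consent, screening and randomization come first, and total participation is 16-18 weeks, so the gap stays just under 18 weeks.

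Both limits assume that the planned timetable is kept.

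**3. Other routes during the gap.**

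| Route | Where | What it provides | Depression score named? |
|---|---|---|---|
| Weekly PI meeting with staff | Section 8 | about 14-18 meetings | No |
| Quarterly monitor meeting (about 92 days) | Section 8 | 98/92 = 1.07 to 126/92 = 1.37, so one or two | No |
| Staff duty to inform the PI | Section 8 | ongoing | No |
| Primary care contact | Section 8 | confirms that exercise is safe | No |
| Routine care, both arms | Section 4 | ongoing | No |
| Instruction session; two or three trainer sessions | Section 4, intervention arm | device use, activity plan, exercise | No |
| Phone consultations | Section 4, intervention arm | 12/2 = 6 calls | No |
| Call after three low-activity days | Section 4, intervention arm | as needed | No |

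The purpose of the phone consultations is "biweekly phone consultation with the research team members to receive guidance and adjustment on activity plans". For controls, no scheduled contact is described between their education and the call after the control period, which covers the Actigraph and diary. Removal "if the research team cannot get contact with the participants for a month" implies some attempts at contact but sets no schedule.

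**4. Upper limit on notifications under a lower trigger.** 20 participants × 2 assessments = 40. If 10% to 50% were positive and untreated at each assessment (an assumption with no source in the documents), the total would be 20 × 0.10 × 2 = 4 to 20 × 0.50 × 2 = 20. Of these, 2 to 10 would come at baseline.

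**The case against.** The strongest reply is that nothing in the documents makes this threshold wrong. They contain no clinical cut-off, no score distribution and no GDS version, so the level at which referral should be compulsory is a clinical judgement. That stands as far as it goes: the documents do not fix the right cut-off. But the protocol already accepts a duty to act on depression answers, and it sets that duty at the one score that cannot be exceeded.

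A second reply is that real duties exist. Staff must bring safety concerns to the PI, the PI must review each participant's safety, and the monitor's remit extends beyond adverse events. A reader might infer that a near-ceiling participant would go unnoticed for months. The documents do not support that: with weekly review and the contacts listed above, such a person may well be picked up. What remains is that none of these routes says which score must be raised, and the contacts specific to the intervention arm do not help controls.

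A third reply is that a lower trigger has a scientific cost. New depression treatment during the 12 weeks could add variability in a 20-person trial that has mood in its first objective and treats negative mood as a possible mediator between sleep and pain. This is fair. It does not outweigh the safety need, but it belongs in the cost.

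Finally, the consent pages are not in the published text and may describe how distress is handled. The point is therefore limited to what is visible.

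**Conclusion.** The point holds for the visible text. The stated rule, followed exactly, requires no referral for an untreated participant one item short of the ceiling, and no GDS result on its own requires one. This is a threshold set too high, with partial general safeguards around it, and it should be changed.

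Its size can be given only in part. The gap to the next depression assessment is 14 to just under 18 weeks. The number of participants affected cannot be estimated, because the documents give neither score distributions nor any measure of how often the general routes would act.

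A reader might also infer that the rule distorts the treatment comparison. It does not: the same rule applies in both arms at the same assessments, and nothing in it biases the efficacy estimate.

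**What to change.** Replace the all-six-at-maximum trigger. Refer an untreated participant to the primary care provider when either of these is met:
- the PROMIS depression items reach a prespecified cut-off clearly below the ceiling, for example 'Always' on several of the six items (one point under the maximum would not mend the problem);
- the GDS is positive by the standard scoring of the version used, with that version named in the protocol.

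The independent safety monitor should agree both cut-offs before enrolment, and both scales should be scored at each of the two planned assessments. The sponsor and monitor should also state whether participants already on treatment are notified.

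The work is a short protocol edit and the scoring of two scales already collected, using the referral route that Section 4 already provides. The costs are:
- some notifications that need no action, within the limit of 40;
- more mental-health information leaving the study, which the consent must cover (whether it already does cannot be checked here);
- possible new depression treatment during the 12 weeks, which could add variability to mood, pain and sleep outcomes. The medication data already collected include antidepressants and should be used to record it.

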The personalized circadian-based activity guideline will be developed based on the individual's typical daily circadian profile, functional status, and preference for exercise. We will advise participants to take afternoon naps (<90 minutes) and avoid napping after 4pm and before 8pm. The research team will work with a certified exercise trainer to develop the personalized physical activity plan for each subject. An afternoon nap of the optimal duration will be advised as healthy napping. All participants will be instructed to nap during this timeframe and to avoid any naps at other times of the day, especially in early evening. The individual's typical circadian profile will be calculated from the two-week baseline Actigraph data. The participant will receive a 30-minute instruction session from the research team session to provide instructions of how to follow the personalized activity guidance and use the study devices. A smartwatch (Fitbit Versa) and a paired smartphone (if the participant does not have a smart phone) will be distributed to participants.

In person training: Participants will receive a 2 or 3 1-hour in person education sessions with the exercise trainer which includes a 20-minute general education on exercise in older adults and a 40-minute education on personalized exercise and participating the study intervention. Session 1 will be within one week after the baseline; Session 2 will be scheduled 2-3 weeks after session 2. All participants in the intervention group will have session 1 and session 2. If the trainer feels the participant need another session to perform the exercise independently, session 3 will then be scheduled as needed. To facilitate the participant's exercise at home, we will provide a set of dumbbell and resistance band for them to use during the study. The education session will be designed using materials from the Go4Life program from the National Institute on Aging (<https://go4life.nia.nih.gov>). The participant will receive a copy of Go4Life program book and can find instructions for all selected exercise in the program book.

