Baseline data collection: After randomization, the research team will distribute an Actigraph to each eligible participant and instruct them to wear it on his/her non-dominant wrist day and night for 14 consecutive days. At the same time, the participants will be instructed to fill out a two-week sleep diary during the days they wear the Actigraph. Pre-intervention (baseline) data collection will take about 45-60 minutes. A research team member will interview eligible participants (up to 30 minutes) for age, race, education, height, weight, life style (tobacco & alcohol use), depression, pain, fatigue, self-reported physical activity, Activity of daily living, self-reported sleep quality, pain, medication use (antidepressant, benzodiazepine, pain and sleep medication), and medical conditions. The research assistant with Phlebotomy training will collect blood sample (5-10ml) from participants.

Post-intervention data collection: After the intervention or control period, a research team member will mail an Actigraph and a two-week sleep diary to the participant's home and contact the participants by phone to provide instructions. The participant will wear the Actigraph and fill out the sleep diary for 2 weeks. A research team member will schedule a meeting with the participant after the Actigraph session to collect post-intervention data. At the meeting, the participants will provide blood sample and be assessed for pain, depression, level of physical activity, and other measures that were collected at screening and pre-intervention following the same procedures. In addition, the participant will be interviewed individually for his/her perspective and experience of the intervention at the meeting for post- intervention data collection. The conversations will be audio recorded and field notes will be taken by a research team member during the interview. We estimate each interview will last no more than 30 minutes. The participant will be asked to answer open-ended questions about the participant's experience of working with smartwatch and the intervention. The voice recordings will be sent to the Production Transcripts for transcription (<https://www.productiontranscripts.com/>). Production Transcripts is a full-service transcription company that specializes in medical and academic research and has a BAA with Johns Hopkins.

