Data management: We will use the REDCap data entry and management system. Data from screening, baseline, intervention sessions, and post-intervention data collection will be entered into forms that the data manager will check for completeness and appropriateness. The data manager will send reports of missing or inappropriate entries to the PI every week for clarification and resolution. **Data that cannot be stored on the REDCap will be stored at either a locked cabinet at the research coordinator (MoCA cognitive screening) / assistants' offices at the JHU School of Nursing or at a folder as electronic files on the JHU box (actigraph data and cognitive assessment, and fitabase data) that could only be accessed by the study team.**

Measurement

Sleep Measures: We will use the Actiwatch to objectively assess nocturnal sleep in terms of total nocturnal sleep time, sleep latency, and wake after sleep onset (WASO); the smartwatch cannot be used to measure sleep due to its need for overnight charging. The Pittsburgh Sleep Quality Index, Epiworth Sleepiness Scale and Insomnia severity index will be used for subject screening and assessing sleep quality subjectively. A two-week sleep diary will be used to confirm Actiwatch-based nocturnal sleep. It will provide information on nap frequency and duration, as well as nocturnal sleep duration. Total nocturnal sleep time is the primary sleep measure, and all others are considered secondary.

Pain Measures: Presence of pain will be determined by affirmative answers to both of the following questions: (1) "Are you currently troubled by physical pain, either all the time or on and off?" and (2) "Has this pain persisted for at least 3 months?" [13]. Older adults answering yes to both questions will then be asked to specify the duration of pain and the pain sites. Pain intensity, severity, and interference with daily life will be measured by two instruments: (1) The brief pain inventory (locations and severity of pain) and (2) PROMIS pain measures (pain intensity, interference, and behaviors). Pain Self-Efficacy will be measured by the Chronic Pain Self-Efficacy Scale.

Fatigue will be assessed by the FACIT Fatigue Scale.

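### Two unexplained missed appointments end study participation, so outcomes and experience interviews that could still be sought from reachable participants are not collected

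*Combined protocol and SAP*

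**What the plan says.** The removal rule stands at the end of Measurement in section 4 and has two triggers. One is loss of contact: "The research team will remove the participants from the study if the research team cannot get contact with the participants for a month". The other applies if "the participant miss two appointments with the research team for no reason". Both take the person out of the study. No separate provision covers someone who stops the intervention but stays in follow-up. The rule does not define an appointment or say what counts as having no reason.

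Under Post-intervention data collection (section 4), "a research team member will mail an Actigraph and a two-week sleep diary" to the home, with instructions by phone. Then "A research team member will schedule a meeting with the participant after the Actigraph session to collect post-intervention data". At that meeting "the participant will be interviewed individually for his/her perspective and experience of the intervention"; no other occasion for the interview is described. Under Sleep Measures, "Total nocturnal sleep time is the primary sleep measure, and all others are considered secondary", and the Actiwatch supplies it.

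Baseline is itself a post-randomisation contact: "After randomization, the research team will distribute an Actigraph to each eligible participant". In the intervention arm, "All participants in the intervention group will have session 1 and session 2", plus an instruction session and biweekly calls. Controls receive general education and no coaching calls.

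Section 2 puts feasibility and acceptability first. Section 7 names no analysis set and no method for missing data.

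**The concern.** The rule acts after randomisation and selects on engagement. Someone who skipped two trainer sessions might still wear a mailed Actigraph, complete a diary and talk about why the programme did not suit them. Under the rule as written they would not be asked.

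Two things are at stake. The first is avoidable loss of post-intervention outcomes in a trial with about 10 people per arm. The second is acceptability evidence drawn mainly from people who engaged, because the interview takes place only at the final meeting. A lesser matter is that the intervention arm has more scheduled contacts and so more chances to meet the rule.

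**Working it through.** The plan states no miss rate, dropout rate or power calculation, so there is no figure of its own to reproduce. What follows is an illustration on stated assumptions.

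**Contacts after randomisation (section 4)**
- Intervention: baseline visit, instruction session, 2 trainer sessions, 12/2 = 6 biweekly calls, post-intervention instruction call, final visit = 12. In person only: 5, or 4 if the instruction session is merged with the first trainer session. The optional third trainer session is left out. Trainer sessions are counted because section 8 lists the exercise consultants among the research team.
- Control: baseline visit, general education, post-intervention instruction call, final visit = 4. In person only: 3.
- Before the final visit, intervention v control: 4 v 2 or 3 v 2 in person, and 11 v 3 if calls count.

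**Assumptions**
- Each contact is missed without excuse with mean probability p = 10% (range 5–15%), equal in both arms.
- A removed person would have attended the final visit at their own attendance rate.
- Miss rates are either the same for everyone, or vary with engagement e ~ N(0,1) through logit P(miss) = a − b·e with b = 0.5, 1 or 2, and a set to keep the mean rate.

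**Chance of meeting the rule before the final visit**

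P(X ≥ 2) = 1 − (1−p)^n − n·p·(1−p)^(n−1). At p = 0.10: n = 2, 0.010; n = 3, 0.028; n = 4, 0.052; n = 11, 0.303.

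At least one of 20 = 1 − [P(X ≤ 1; n_I) × P(X ≤ 1; n_C)]^10.

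**Expected number lost who would have attended the final visit**

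With equal miss rates this is 10 × 0.9 × [P_I + P_C]:
- 4 v 2: 9 × (0.0523 + 0.0100) = 0.56
- 3 v 2: 9 × (0.0280 + 0.0100) = 0.34
- 11 v 3: 9 × (0.3026 + 0.0280) = 2.98

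**The same, requiring the baseline visit to have been attended**

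Without a baseline value, and unless that visit is rescheduled, a person adds nothing to the Time × Group comparison in 7.3. One contact is therefore fixed as attended, and two misses must fall among the rest. With equal miss rates:
- 4 v 2: 10 × 0.9 × 0.9 × (0.0280 + 0) = 0.23
- 3 v 2: 10 × 0.9 × 0.9 × (0.0100 + 0) = 0.08
- 11 v 3: 10 × 0.9 × 0.9 × (0.2639 + 0.0100) = 2.22

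Results at 10% over b = 0 to 2:

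| Contacts before final visit | At least one of 20 (b = 0) | Expected loss, all | Expected loss, baseline attended |
|---|---|---|---|
| 4 v 2 (in person) | 47% | 0.6–0.7 | 0.22–0.26 |
| 3 v 2 (in person) | 32% | 0.3–0.5 | 0.08–0.10 |
| 11 v 3 (calls count) | 98% | 2.0–3.0 | 1.2–2.2 |

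Over miss rates of 5–15% the expected loss for all becomes 0.2–1.2, 0.1–0.8 and 1.0–4.8 of 20.

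**Bias from unequal exposure**

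Suppose no true effect, and a correlation r = 0.3–0.5 (assumed) between engagement and outcome change. Then bias = r × (mean e of retained intervention − mean e of retained control), using all contacts including the final visit.
- Both arms at 10%: 0.01–0.04 SD (5 v 3), 0.01–0.02 SD (4 v 3), 0.06–0.14 SD (12 v 4).
- Intervention 5%, control 10%: −0.02 to 0.00 SD in person, 0.01–0.04 SD if calls count.
- Standard error of the group difference: √(1/10 + 1/10) = 0.447 SD.

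**The case against.** Several objections have force.

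- A reader might infer that data are thrown away. The documents do not say so: the rule stops future collection and is silent on data already held. Uncollected is the right word.
- A reader might extend the point to the one-month no-contact trigger. Those people can seldom be recovered, so that trigger is no part of the point.
- A reader might infer that the efficacy estimate is biased in favour of the intervention. The documents do not establish this. The bias is small, and its sign depends on equal miss rates and on engaged people doing better. Section 10 gives only the intervention arm weekly incentives and a Fitbit to keep on completion. Section 4 adds a call after three low-activity days. Either could lower that arm's miss rate, and the in-person bias then vanishes or reverses.
- The larger loss figures need the calls to count as appointments. The protocol calls them consultations, so that reading is doubtful. On the in-person reading the chance at 10% that nobody meets the rule before the final visit is 53–68%.
- The miss rate, the contact count and later attendance by removed people are all assumed. Counting only about 10 v 2 contacts, for example, gives removal of 26% v 1% at 10%.
- Section 8 has the investigator monitor retention and adherence, and 7.2 describes feasibility data. Removals could be reported there, though 7.2 does not name them.

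These objections reduce the size of the point. They do not alter the text: removal is from the study, and nothing provides for seeking outcomes or an interview afterwards.

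**Conclusion.** The point holds as a minor one. As written, two unexplained missed appointments end outcome collection and forfeit the experience interview, including for people who can still be reached.

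On the in-person reading the expected cost is under one participant of 20 at a 10% miss rate. It reaches two to three only if calls count. For the Time × Group analysis the cost is smaller still, because some of those lost would have no baseline value. All these figures rest on the assumed miss rate and on removed people attending the final visit at their own rate.

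The main reason to act is the acceptability aim. The interviews most likely to be lost are those with the least engaged participants, and that does not depend on the bias model. The unclear scope of the rule is a second reason, since whether calls count changes its reach several-fold.

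**What to change.** State in section 4 that meeting the missed-appointment rule, whatever it does to intervention contact, does not end outcome collection. Say whether phone calls count as appointments, and what makes a miss unexplained. Suggested wording for section 4, cross-referenced in section 7:

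> Unless consent is withdrawn, every randomised participant who can be reached is sent the post-intervention Actigraph and diary, invited to the post-intervention visit and interview, and analysed in the assigned arm in 7.3 where data allow. The number meeting the rule is reported by arm.

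The cost is the wording plus, for each person concerned, a mailing with some risk of device loss, a visit invitation, the $50 gift card and interview transcription. That is about 0–1 people if only in-person contacts count: at 10%, 10 × (0.052 + 0.010) = 0.6 are expected to meet the rule before the final visit. It is roughly 2–5 if calls count: 10 × (0.303 + 0.028) = 3.3 at 10%. Some will not respond, and the estimated effect may come out slightly smaller.
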